# **Appendix 2: Patient Questionnaires for Visit 2**

# Patient Oral Health Questionnaire - Visit 2 – Part A

If you have trouble completing this questionnaire, please ask a member of staff to assist you.

**1.** How many times per day do you now regularly brush your teeth? (*Please tick one box only*)

	Less than once a day					
	Once a day	1				
	Twice a day					
	More than twice a day	7				
2.	. When do you now normally brush	n your teetl	h? (Please tick all that a	pply )		
	In the morning					
	In the evening					
	During the day					
3.	Do you usually brush your teeth (F Before breakfast	Please tick	one box only)			
	Neither before or after breakfast	H				
	After breakfast	H				
	Both before and after breakfast	H				
4.	Do your gums bleed now when yo	bu brush yc	our teeth?			
	NO					
5.	. Do you think you have bad brea	ath now?				
	NO					
6.	. Do you use any of the following ac	dditional te	eeth cleaning aids now f	? (examples )	are shown belo	w,
pie	Dental Floss Flosset	ave usea or ttes	Single tufted brush	e, tick none) Interdental	hrushses (e ø Tel	Pe)
	Air flosser (e.g Phillips Airflos	oss Plus)	Water flosser (e.g Wate	erpik)	None	
			And and a second	-	X	

Page 16 of 23

- 7. If you have indicated you have used an additional cleaning aid, how often did you use them?
  Daily

  Weekly
  Occasionally

  8. Are you currently concerned about your oral health?

  YES
  NO

  9. Has your diet changed since you started the study with us?

  Yes
  No
  No
  No
  No
  No
  No
  No
  No
- **10.** Was the pictorial report of your oral health provided in this study useful for you?

.....

Very useful	
Fairly useful	
Neither useful or not useful	
Not useful	
Not sure	
How often did you refer o your pi	ctorial report provided in this study?
Daily	

How?...

11.

Weekly

Didn't refer to it

12. Are you currently concerned about your oral health?

YES	
NO	

**14.** If yes, what are your concerns?

Condition of teeth	
Function of teeth	
Appearance	
Breath	
Sensitivity	
Other/Not sure	
None	

**15.** How would you rate your current oral health now?

Excellent	
Very good	
Good	
Fair	
Poor	
Not sure	

16. Are you motivated in maintaining oral health now?

	Very motivated	
	Fairly motivated	
	Neither motivated or not motivated	
	Not motivated	
	Not sure	
17.	Has your motivation to maintain you	r oral health changed since you started the study with us?
	Yes N	Not sure
	How?	

so

#### Patient Oral Health Attitudes Questionnaire- Visit 2 – Part B

On a scale of 1 to 10, with 1 as 'Not at all' and 10 as 'extremely so' please rank the following statements accordingly:

- 7. Do you think bleeding gums and gum disease is a serious health concern 1 2 3 4 5 6 7 8 9 10 Not at all Extremely SO 8. If my bleeding gums are left untreated the likelihood that I will develop gum disease in the future is high 1 2 3 4 5 6 7 8 9 10 Not at all Extremely
- 9. Following my Oral Health plan over the last 4 weeks has improved the health of my mouth and reduce my risk of developing gum disease

1	2	3	4	5	6	7	8	9	10
Not at all									Extremely so

10. I know I can continue to follow my Oral Health plan in the future

1	2	3	4	5	6	7	8	9	10
Not at all									Extremely
									SO

11. Following my Oral Health plan will be difficult to maintain.

1	2	3	4	5	6	7	8	9	10
Not at all									Extremely so
12. My gun	n disease	concern	s me						
1	2	3	4	5	6	7	8	9	10
Not at all									Extremely so

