#### Secondary Objectives

- Patient perceptions of effectiveness of a having a pictorial report of their oral health as part of their dental care
- Patient attitudes to oral health measured at baseline and 4 weeks
- Participants' understanding of gingival health vs gingival disease
- Assessment of the accuracy of the intra-oral camera's ability to assess plaque levels compared to the clinician using traditional techniques using dye

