#### Secondary Objectives

- Patient perceptions of effectiveness of a having a pictorial report of their oral health as part of their dental care at Visit 1 and Visit 2
- Patient attitudes to oral health measured at Visit 1 and Visit 2
- Participants understanding of oral health vs oral disease at Visit 1 and Visit 2
- Assessment of the accuracy of the intra-oral camera's ability to assess plaque levels compared to the clinician using traditional techniques using dye

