#### **Statistical Analyses**

Descriptive statistics (number of subjects, mean, standard deviation, median, minimum and maximum for continuous variables, and frequency and percentage for categorical variables) will be provided for demographic and baseline data.

A mixed effects model with random effects for participants and fixed effect for treatment. The 95% CI along with the mean difference (of change from baseline) in mean plaque levels at 4 weeks for each group will be reported. Adjustment for covariates (e.g. gender, age) will be included in the model.

The primary outcome will also be summarized (using summary statistics) by intervention group, and where appropriate assessment points. Where appropriate and data permitting covariates (e.g. age, gender) will be included in the model. For each secondary outcome, similar analyses will be performed as the primary outcome using a generalized linear model with an appropriate link function depending on the nature of the outcome. Appropriate 95% confidence intervals and p-values will be generated.

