## Patient Oral Health Attitudes Questionnaire- Visit 1 – Part B

On a scale of 1 to 10, with 1 as 'Not at all' and 10 as 'extremely so' please rank the following statements accordingly:

1.	Do you	think blee	eding gur	ns and g	um disea	ase is a s	serious	health	conce	ern
	1	2	3	4	5	6	7	8	9	10
N	lot at all									Extremely so
2.	lf my ble disease	eding gui in the futi	ms are le ure is hig	ft untrea h	ted the li	kelihood	that I	will dev	velop ç	gum
	1	2	3	4	5	6	7	8	9	10
N	lot at all									Extremely so
3.	Followin mouth a	ig my Ora nd reduce	l Health p e my risk	olan over of devel	r the next oping gu	t 4 week m disea	s will ir se	nprove	the he	ealth of my
	1	2	3	4	5	6	7	8	9	10
N	lot at all									Extremely so
4.	l know l	can follow	v my Ora	l Health I	plan ove	r the nex	t 4 wee	eks		
	1	2	3	4	5	6	7	8	9	10
Ν	lot at all									Extremely so
5.	Followin	ig my Ora	l Health p	olan will	be difficu	ult to do.				
	1	2	3	4	5	6	7	8	9	10
Ν	lot at all									Extremely so
6.	6. My gum disease concerns me									
	1	2	3	4	5	6	7	8	9	10
Ν	lot at all									Extremely so

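### Three of the six attitude items are reworded between visits and refer to an undefined oral health plan; for one pair the change from baseline is not a change in attitude, and for the other two it is hard to interpret

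*Protocol*

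**What the plan says.** The Protocol's Secondary Objectives list "Patient attitudes to oral health measured at baseline and 4 weeks". The secondary list under Outcomes repeats this as "Patient attitudes to oral health measured at Visit 1 and Visit 2".

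Statistical Analyses then states: "For each secondary outcome, similar analyses will be performed as the primary outcome using a generalized linear model", with a link function suited to the outcome. The estimate named for the primary outcome is "The 95% CI along with the mean difference (of change from baseline) in mean plaque levels at 4 weeks", to be reported for each group.

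The instrument is Part B of the patient questionnaires in Appendix 1 (Visit 1) and Appendix 2 (Visit 2). It has six statements at each visit, each rated from 1 to 10; the Visit 2 form numbers them 7 to 12. Two of the Visit 2 statements are "Following my Oral Health plan over the last 4 weeks has improved the health of my mouth" (item 9, which goes on to the risk of gum disease) and "I know I can continue to follow my Oral Health plan in the future" (item 10).

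Study Design and Items provided to patient describe what participants receive. Both arms get oral hygiene instruction (OHI) at Visit 1. The test arm also gets a pictorial report, a leaflet and a mouth mirror at Visit 1. Controls get those items only after the Visit 2 assessments.

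**The concern.** A change score needs the same quantity measured twice. If the question changes between visits, the difference mixes any real change with the effect of the new wording. A participant who expected a great deal at Visit 1 and saw a modest result at Visit 2 would show a fall on pair 3/9 with no change in attitude. A participant with low expectations and a pleasant surprise would show a rise.

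The three reworded pairs are also the three that ask about the participant's oral health plan. The Protocol does not say what that is, so it does not fix what the participant is rating.

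At stake is the reading of one secondary outcome. A rise or fall within an arm on these items could be published as a shift in attitude when it reflects only the rewording.

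**Working it through.** No figure in the Protocol bears on this point, so the first step is to set the two forms side by side.

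| Pair (Visit 1/Visit 2) | Visit 1 asks about | Visit 2 asks about | Same wording? | Cites a plan? |
|---|---|---|---|---|
| 1/7 | seriousness of bleeding gums and gum disease | the same | yes | no |
| 2/8 | likelihood of gum disease if bleeding is untreated | the same | yes | no |
| 3/9 | expected benefit over the coming 4 weeks | benefit perceived over the past 4 weeks | no | yes |
| 4/10 | confidence in following the plan for 4 weeks | confidence in continuing it, with no end date | no | yes |
| 5/11 | difficulty of doing it | difficulty of keeping it up | no | yes |
| 6/12 | concern about own gum disease | the same | yes | no |

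Three of six pairs (50%) are reworded, and the same three, and only these, cite a plan. The text of the Visit 1 form is partly broken by extraction, but the sense of each item can be recovered. The 7–12 numbering is not counted as an error.

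**Degree of mismatch.** Pair 3/9 changes construct, from expectation to perceived result. Pairs 4/10 and 5/11 keep their constructs (confidence, difficulty) but move from starting to maintaining.

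**The plan.** The term appears only in the two Part B forms. The Introduction mentions written coping plans, but as background literature and not as part of the intervention.

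**Effect on the estimates.** Let δ be the true mean change in an arm and w the shift due to wording.
- Within an arm: expected mean change = δ + w.
- Between arms: expected difference in change = (δ_test − δ_control) + (w_test − w_control).

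If w is the same in both arms, it drops out of the second line but not the first. A simulation illustrates this. Its assumptions, none from the Protocol except 10 per arm, are: Visit 1 mean 6 and SD 2, SD of change 1.5, no true change, a wording shift of 1 point in both arms, and 20,000 repeats. Mean change was 1.000 in one arm and 1.003 in the other, all of it artefact. The between-arm difference was −0.003, which is zero apart from simulation error.

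**Noise between arms.** With equal variances at the two visits and correlation ρ between them, SD(change)/SD(Visit 2 value) = √(2(1 − ρ)). The Protocol gives no ρ, so a range is shown:
- ρ = 0: √2 = 1.41
- ρ = 0.2: √1.6 = 1.26
- ρ = 0.5: √1 = 1.00

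Subtracting the Visit 1 answer therefore adds noise when ρ is below 0.5, which is more likely when the two questions differ.

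**Order at Visit 1.** The Visit 1 list puts the questionnaire after randomisation and before OHI. The Study Design narrative mentions it after OHI. On the list order, participants rate a plan before they have had any instruction. On the narrative order, the Visit 1 answers may already differ between arms. The difference in change is then the Visit 2 difference minus a Visit 1 difference that the intervention itself produced, which is biased as a measure of the intervention's effect.

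**The case against.** The strongest reply has five parts.

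- **The change score is inferred.** The change-from-baseline sentence names plaque, and item-level modelling is commonly left to an SAP, which may exist. This is right as far as it goes. Still, an outcome measured at baseline and 4 weeks and analysed like a change-from-baseline primary outcome is most naturally read as a change score. The wording is fixed in the Protocol's appendices, and an SAP cannot make two different questions the same.
- **The trial compares arms, and both get the same forms.** This stands for any shift common to both arms, as the working shows. It does not protect within-arm change.
- **Participants will take the plan to mean the instruction they received.** They may, and both arms do receive instruction. A reader might infer that the items refer to something no one has, or that controls have nothing to rate; the documents do not support that. What stands is that the Protocol does not define the term, and that only test participants also hold a report, leaflet and mirror before Visit 2. Whether the arms would read the term differently is conjecture.
- **Adapting items for week 4 is sensible.** This is fair for 4/10 and 5/11. A reader might infer that all three pairs are equally unusable, but only 3/9 plainly changes construct.
- **Visit 1 answers remain useful.** A covariate need not have the same wording as the outcome. This stands, provided the form is completed before any arm-specific content.

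Because a high score on the difficulty item is unfavourable, a reader might also infer that a total score would be distorted. The Protocol mentions no total, so there is nothing to correct on that count.

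**Conclusion.** The point holds and is worth acting on, within limits. The change score for pair 3/9 is not a change in attitude. Those for 4/10 and 5/11 are hard to interpret, though less so. Within-arm change on all three is confounded with the wording. Between arms the harm is mainly added noise, if the correlation between visits is below 0.5, and bias if the Visit 1 form is completed after arm-specific instruction.

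The conclusion assumes that attitudes will be analysed as change from baseline, which is the natural but not the explicit reading of Statistical Analyses. The size of any wording shift is unknown; the 1 point used above only illustrates the mechanism. The point concerns three items of one secondary outcome in a 20-person pilot sized for estimation, and it does not touch the plaque or gingival results.

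**What to change.** 1. Report change from baseline only for pairs 1/7, 2/8 and 6/12.
2. Compare items 9, 10 and 11 between arms as Visit 2 values. Keep Visit 1 items 3, 4 and 5 as separate expectation measures. Use them as covariates only if they are completed before OHI, and before the images are explained to the test arm.
3. In both arms and at both visits, replace the reference to a plan with wording that names the oral hygiene advice given in the study. If the Visit 1 form comes before that advice, word it as advice still to be given.
4. Reconcile the Visit 1 list with the Study Design narrative on when the questionnaire is completed. The identically worded pairs also need a true baseline.

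The cost is a few words in the study questionnaires and one sentence on analysis. The downside is small: three items of one secondary outcome lose their change score. Their Visit 1 answers are kept.

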## Appendix 3: Standard Images of oral health and oral disease

Do the images below, in your opinion, show oral health or oral disease? Indicate which image you think represents your current oral health *Please 'tick' the box which represents your answer for each image* 

	IMAGE 1	IMAGE 2	IMAGE 3
Health			
Disease			
Do not know			
Represents my current oral health			

# **IMAGE 1**

# **IMAGE 2**

**IMAGE 3** 

## **Appendix 4 – Clinical Assessments**

#### Plaque Scores

Plaque scores will be recorded at Visit 1 and 2 following the method established by O'Leary et al (1972). Plaque will be scored using binary code as follows:

'NO' plaque = 0

'YES' plaque present = 1.

#### **Gingival Health**

Gingival health will be assessed using the Modified Gingival Index (Lobene, 1986) which is a non-invasive visual evaluation of gingival health. Each site (2 per tooth) will be classified as healthy or exhibiting gingivitis. If the site exhibits gingivitis the MGI index will be used to assess the degree of inflammation at 2 sites (buccal and lingual/palatal) of all scorable teeth and scored on a 5-point scale as follows:

- 0 = normal (absence of inflammation)
- 1 = mild inflammation (slight change in colour, little change in texture) of any portion of the gingival unit
- 2 = mild inflammation of the entire gingival unit
- 3 = moderate inflammation (moderate glazing, redness, oedema, and/or hypertrophy) of the gingival unit

4 = severe inflammation (marked redness and oedema/hypertrophy, spontaneous bleeding, or ulceration) of the gingival unit.

Bleeding on probing is assessed using the gingival bleeding index (BOP) as described by Ainamo & Bay (1975) and will also assess gingival health. A periodontal probe with a 0.5 mm diameter tip is inserted into the gingival crevice and swept from distal to mesial, around the tooth at an angle of approximately 60° while in contact with the sulcular epithelium. For each tooth assessed, a binary recording of either YES (bleeding observed) or NO (no bleeding observed) for bleeding will be made at 4 sites per tooth. The proportion of bleeding sites compared to all examined sites will provide the percentage of bleeding per participant.

# Appendix 5: Oral Health Assessment using an Intra-oral camera (Soprocare Acteon® (PERIO mode and DAYLIGHT mode))

The pictorial record of participant plaque and gingival condition will be assessed/obtained using Soprocare Acteon® (PERIO mode and DAYLIGHT mode).

The PERIO mode also uses the phenomenon of fluorescence but this time combined with selective chromatic amplification.

When this mode is in use, the tooth is illuminated with both blue LEDs (for fluorescence) and white LEDs (to maintain the relief) in order to recover the fluorescence emitted in return by pigments present in dental plaque.

To highlight gingival inflammations, SOPROCARE uses the settings of selective chromatic amplification to enhance this pathology.

#### **Example of a pictorial Patient Report**

The measurements must not be used for diagnostic purposes. ACTEON can not be held responsible for the content of this document.
